First, prior to participation, participants are informed of all procedures, and both they and their parents/guardians must proceed through an informed consent process and provide assent or consent stating that they understand and agree to the procedures. Therefore, it is likely that any individual who would be made uncomfortable by answering questions about alcohol use and other health behaviors would decline to participate, as example questions are outlined in the consent form. **Second**, similar to the PI's prior NIH-funded work, and as done in other adolescent addiction studies (e.g., Chung et al., 2005; Schmiege et al., 2009), to ensure adolescent's confidentiality, all data will be identified with a numeric code and stored in a locked cabinet separate from consent forms and confidential locator forms. In addition, adolescents' data will be retained by the PI and maintained in a separate cabinet. Consistent with the PI's prior NIH funded work, the confidential locator forms will be destroyed upon participants' completion of the final follow-up. Like the locator forms, all videotapes used for paradigm verification will be destroyed when the final participant completes his/her final follow up. **Third**, our magnetic resonance (MR) technicians are highly experienced and have received specific training through OHSU's Advanced Imaging Research Center to prevent accidents in the fMRI scanner. Both the trained study staff

and the MR technician provide a rigorous screening to ensure that participants do not have any metal on or inside their bodies prior to entering into the scanner. This screening includes the use of a metal detection wand (similar to those used in airports) as a final check. In addition, access to the magnet is limited to prevent others from bringing in metallic objects. We also screen for claustrophobia and provide individuals with earplugs to reduce the amount of noise they experience. It is still possible that individuals may feel anxious in the scanner, but they are in constant communication with the experimenters (i.e., through headphones and an intercom system) and can stop the experiment (i.e., using an emergency squeeze bulb) and be removed at any time if they are feeling too anxious to continue. **Fourth**, we have not encountered any reticence by the youth to disclose their substance use and related risk behavior. Completion of the assessment measures has minimal risk and adolescents are notified that they may skip questions that are distressing for them to answer without it negatively impacting their compensation or status within the study. **Fifth**, our team is highly experienced at working with youth who are engaging in illegal behaviors, including substance use. We will continue to take exhaustive steps to protect youth's privacy in this study. Consistent with our prior work, we have obtained a federal Certificate of Confidentiality to serve as an additional layer of protection.

10) Risks and Benefits

a) Risks to Subjects

There are five potential risks associated with participation and every effort will be made to reduce potential discomfort. **First**, there is the potential discomfort involved in answering questions about sensitive topics, including alcohol use behavior. **Second**, there is the risk of breach of confidentiality of behavioral, neuroimaging, and/or genetic data. **Third**, while the fMRI procedures involve no pain or invasive techniques, individuals occasionally find the partially enclosed space and/or the noise of the scanner uncomfortable. Adverse events associated with fMRI can involve the action of the magnetic field on metallic objects. For example, metallic objects on or inside the body of participants or foreign metallic objects that are brought into the room with the magnet may injure participants. **Fourth**, standard risks for adolescent health risk behavior research often include discussions regarding illegal activities (e.g., discussions about drinking, as alcohol use under the age of 21 is illegal). **Fifth**, another standard risk includes the desire of parents/guardians to obtain data collected in this study regarding adolescents' health behavior and other activities. However, as has been done in the PI's prior research, this risk will be minimized through active efforts to protect the confidentiality of adolescents' data, including obtaining a Certificate of Confidentiality from NIH (which we have done), and the maintenance of data in locked cabinets and secure, encrypted servers at OHSU, which will only be accessible by the PI and trained research staff.

b) Potential Benefits to Subjects

This study is expected to add critical data that will add to the knowledge base to improve alcohol use treatment for binge drinking adolescents. Given the minimal risk to participants and the greater possibility of long-term benefit to the participant and the greater knowledge base, the risk/benefit ratio seems reasonable. As a part of this study, all participants will have the opportunity to examine their own alcohol use behavior in the context of completing measurement instruments, have the opportunity to work with a trained counselor, and receive a widely-used, empirically supported alcohol use treatment, which may help facilitate their efforts to reduce their problem drinking behavior. The costs associated with participating have been minimized via the consent procedures, procedures for maintaining confidentiality, and safeguards during the fMRI component. The minimal costs associated with participation in this research are reasonable in relation to the anticipated benefits to the participants themselves.

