Prior to beginning any study procedures (both during the phone screen and reiterated in person), the trained RAs will inform adolescents (and for youth age 17 and under, also their parents/guardians) that researchers at OHSU are trying to improve our understanding of adolescent health behavior and related consequences, and that their participation will help us develop better programs to help teenagers like them stay healthy. Adolescents will be told that some of the questionnaires will ask questions about sensitive topics, such as about alcohol use behaviors (which is illegal for everyone under the age of 21) and sexual activity. They will also be informed that the researchers are interested in understanding how health behaviors affect the body and the brain, thus, a number of measures, including brain imaging, saliva, their thoughts on alcohol use, and other health risk and related behavior, will be collected. All procedures will be fully explained. The staff member will be explicit that participation is completely voluntary, meaning that youth can decide to opt out of the research protocol at any time they wish without repercussion, and that opting out does not affect their involvement with any community or justice programs in which they may be involved.

Adolescent and parent consent will be obtained, but adolescents will have the opportunity to speak with study staff about the study details without a parent present before signing the consent form. This is to diminish discomfort that adolescents might feel in being asked to participate when their parents are present, as asking them to agree to participate in front of their parents might not allow them to ask important questions about the study without violating their privacy.

If the adolescent agrees to participate, the RAs will seek OHSU-approved informed (written) assent from the adolescents, as well as informed telephone consent from parents/guardians (for youth ages 17 and under) prior to their commencement of Session 1. Minors will not participate if they do not assent to participate, even if a legal guardian has consented. If a minor turns 18 during the course of the study, then they will be asked to consent for themselves by re-signing the consent form as an adult.

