For parent/guardians requesting to consent through email but unable or unwilling to navigate the REDCap system, staff will send a PDF of the full consent form to the parent/guardian's preferred email address. The email will describe how to complete the form, and request that the parent/guardian call lab staff upon receipt with questions and concerns. The email will explicitly state that it the parent/guardian's right to receive a consent review by phone to ensure they understand the key points. Parent/guardians will have the option to return the completed signature page by email, or to send it with their child to their child's first study visit, if the parent is not accompanying the youth to OHSU. See the **Parent Consent Email Template** for exact wording of the email.

If a parent is accompanying their child to the first study visit, the parent can consent in person before the youth begins Session 1.

At each point of data collection, research staff will reiterate the voluntary nature of all aspects of the study (behavioral, neuroimaging, saliva sampling), and participants' right to refuse to answer any questions, and cease participation in any aspect of the study at any time without any type of recrimination.

6) Procedures

Session 1 components.

Behavioral Assessment. To improve accessibility, all Session 1 components will be delivered at OHSU in a confidential room dedicated to our team for this purpose. The trained RA will conduct the behavioral assessment using Audio Computer-Assisted Self-Interviewing (ACASI) on an individual laptop. ACASI has proven to be a reliable way to obtain survey data assessing health risk behaviors (Williams et al 2000). ACASI technology allows survey questions to be displayed on a laptop computer screen while respondents hear the spoken text over headphones. A saliva sample will be collected during this time for DNA banking.

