Session 2 MI. The second session will begin with an open-ended query of participant's experience during the scanning protocol. Next, the counselor will check in with the youth to see how their drinking went in the intervening week. The counselor will then provide personalized feedback (PF) of the youth's alcohol use and alcohol-related problems as derived from their baseline assessment data. Following this, the counselor will actively and collaboratively engage youth in the development of discrepancy (exploring how their drinking fits with youth's immediate and long-term goals), the identification of high-risk situations and triggers for drinking, and an exploration of strategies to manage those risks and triggers. Similar to the first MI session, the counselor will close Session 2 with a summary of the session and a broad and non-judgmental query of how the youth would like their alcohol use to be in the near future (e.g., *"Tell me how you would like your drinking to look when our team sees you again in 3 months."*)

Session 2 Brief Adolescent Mindfulness (BAM): Like the second MI session, the counselor will start with an open-ended query of the participant's experience during the scanning week. Next, the counselor will check in with the youth to see how their drinking went in the intervening week. The counselor will proceed by reviewing any instances of mindfulness utilized by the participant and discuss the connection between experiencing anxiety, worry, and/or stress and substance use. The counselor will help problem solve barriers to practicing mindfulness in the youth's life. In addition, the counselor will end the session with a review of mindfulness concepts and tools, and provide the participant with a handout outlining accessible mindfulness resources (e.g., free apps and websites with guided meditations).

Total length of participation. All youth will participate 5 times over the course of 12 months (Baseline Assessment/Intervention Session 1, fMRI/Intervention Session 2, 3-month follow-up with second fMRI, 6-month follow-up, 12-month follow-up).

Circumstances for withdrawing a subject without their consent. If a subject is disruptive, uncooperative, threatening or physically violent towards other subjects or research staff during a participation session, their participation will be terminated. If a subject chooses to stop participating

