for any reason, the youth's participation will be terminated. If a parent chooses to have their adolescent stop participating for any reason, the youth's participation will be terminated.

Procedures for withdrawal, including partial withdrawal. If a youth withdraws from the research, we will continue to retain the data collected until that point, unless they specifically request removal of their data from the study. In this event, we will destroy all of their data. Subject identifying information and any video recordings will be destroyed following the final study participant's completion of his or her 12-month follow up; therefore, if a participant requests that his or her data be removed following the conclusion of the study, we may not be able to complete the request as the data will no longer be identifiable as coming from a particular research subject.

7) Data and Specimens

a) Sharing of Results with Subjects

Incidental findings from Imaging. The MRI scan is being done to answer research questions, not to examine individual brains for medical reasons. This MRI scan is not a substitute for a clinical scan (the type a doctor would order). The research scan may not show problems that may be picked up by a clinical MRI scan. If we find an abnormality that appears to require urgent follow-up after review by a neuroradiologist on the study team, we will contact the participant by phone to help answer questions, recommend that the participant contact their doctor to schedule a clinical scan, and assist in getting the right follow-up care for the individual. It is possible that the individual could be unnecessarily worried if a problem were suspected, but not actually found. Our research team is always available to answer any questions the individual may have about their scan.

Incidental findings from pregnancy testing. Parents or guardians of a child participating in this study may be told the results of the child's pregnancy test if the child is younger than 15. If the child is 15 or older the pregnancy test result will be released to the child. It will be up to her whether or not it is released to the parent or guardian. However, if the Principal Investigator believes that the child is not receiving adequate medical care for the pregnancy, she will refer the subject to a place where the participant can get the proper care.

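### The parent-stop rule has no age limit, and removal for being uncooperative carries no outcome-only follow-up: an avoidable and possibly selective loss of drinking outcomes

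*Combined protocol and SAP*

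**What the plan says.** All references are to the combined protocol and SAP.

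- **Section 6, circumstances for withdrawing a subject without consent.** Staff-initiated removal is mandatory: "If a subject is disruptive, uncooperative, threatening or physically violent towards other subjects or research staff during a participation session, their participation will be terminated". A youth's own decision to stop has the same result, as does a parent's: "If a parent chooses to have their adolescent stop participating for any reason, the youth's participation will be terminated".
- **Section 6, next paragraph.** It opens "Procedures for withdrawal, including partial withdrawal. If a youth withdraws from the research, we will continue to retain the data collected until that point". The rest covers destruction of data on request and the date after which destruction may be impossible. It says nothing on how a partial withdrawal is handled.
- **Section 5b (inclusion criteria) and Section 5f (Consent Process).** Parental consent is required for youth aged 17 and under. On reaching majority: "If a minor turns 18 during the course of the study, then they will be asked to consent for themselves".
- **Section 5f, closing paragraph.** Participants are reminded at each data collection that they may "cease participation in any aspect of the study at any time without any type of recrimination".
- **Section 9.** Youth are told "they may skip questions that are distressing for them to answer without it negatively impacting their compensation or status within the study".
- **Section 5d and Section 6, Follow-Up Procedures.** The 6- and 12-month assessments are offered by phone and REDCap. At 3 months, youth who cannot travel to campus for the visit and scan are offered remote measures instead.
- **Section 8.** The analyses take BOLD from the baseline scan and outcomes from 3, 6 and 12 months. Allowance for loss is an inflation for 16% attrition. No missing-data method is given.

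**The concern.** Two stated rules can remove youth from outcome follow-up when they need not be removed.

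First, the parent rule sits under a heading about withdrawal without the subject's consent and carries no age limit. Followed literally, it ends the participation of an 18- or 19-year-old who has given their own consent and wishes to continue. That does not fit the plan's own consent rules.

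Second, removal for being uncooperative is compulsory, the word is not defined, and nothing provides for outcome-only follow-up afterwards. The motivational interviewing arm treats youth resistance as something to work with (Section 6, Intervention Overview), so some friction in sessions is expected. Staff make the judgement after randomization. Youth removed this way may plausibly differ in both neural response and later drinking. If they do, losing them could distort the BOLD-drinking association behind Hypotheses 2 and 3 as well as reduce numbers.

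The outcomes at stake are the Time-Line Follow-Back (TLFB) binge-drinking days and the Rutgers Alcohol Problems Index (RAPI). Both form the problem-drinking index in Section 8, and the plan already has a remote route for collecting them.

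**Working it through.** **1. Parent rule against consent rules.** Section 2 describes the whole sample as adolescents aged 14-19, so the word adolescent in the parent rule does not by itself restrict it to minors. The enrolment ages are 14, 15, 16, 17, 18 and 19. Two of these six year-ages (18 and 19) are above the parental-consent limit at entry. A youth enrolled at 17 reaches 18 within a year, and follow-up lasts 12 months. This describes the reach of the rule, not the share of participants, since the age distribution is not given. For these youth Section 5 places consent with the participant, while Section 6 lets a parent end participation.

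**2. Uncooperative conduct against permitted refusal.** Section 9 protects skipping questions, and Section 5f protects stopping any one aspect. Section 6 requires removal of an uncooperative youth. No sentence separates the protected refusal from the conduct that triggers removal.

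**3. Partial withdrawal.** The heading names it, but the paragraph deals only with data already collected. Those data are kept unless the youth asks for removal, in which case all are destroyed. The loss from termination is therefore of future outcomes.

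**4. What a termination loses, by timing.** Section 6 places the first scan in the second visit, before the second counselling session.

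| Participation ends | Baseline BOLD available? | Outcome visits lost |
|---|---|---|
| At Session 1 | No | 3, but without a scan they could not enter Hypotheses 2 or 3 |
| At Session 2, after the scan | Yes | Up to 3 (3, 6, 12 months) |
| At the 3-month visit | Yes | 2, or 3 if that visit's measures are not done |
| Between 6 and 12 months | Yes | 1 |

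**5. Sample size.** Inputs from Section 8: 204 evaluable for Hypothesis 3, 16% loss, power 0.80, two-sided alpha 0.05.

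- 204 / (1 - 0.16) = 242.86, rounded up to 243. The plan's figure reproduces.
- 243 x 0.84 = 204.1 completers, so 243 - 204 = 39 losses are budgeted, from all causes.

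The documents do not say how many youth these rules would remove. If the removals fall within the 16%, N is unaffected and only selectivity matters. If they come on top of it, the effect for an assumed extra loss e is:

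- completers = 243 x (0.84 - e)
- enrolment needed = 204 / (0.84 - e), rounded up
- approximate power = Φ((1.960 + 0.842) x √(completers / 204) - 1.960), anchored at the plan's 0.80 for 204

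| Assumed extra loss e | Completers of 243 | Enrolment to keep 204 | Approximate power |
|---|---|---|---|
| 1 point | 201.7 | 246 | 0.796 |
| 2 points | 199.3 | 249 | 0.791 |
| 3 points | 196.8 | 252 | 0.786 |
| 5 points | 192.0 | 259 | 0.776 |
| 10 points | 179.8 | 276 | 0.749 |

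This table only gives scale. A few points of extra loss would cost little power, so the argument for change rests on avoidability and possible selection.

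**The case against.** The strongest reply is that the plan already tolerates partial participation. A reader might infer that Section 6 flatly contradicts the right to stop one aspect. It does not. A youth who chooses to stop participating is most naturally one who leaves the study, and any reason is not the same as any component. Section 9 keeps a youth's status when questions are skipped, Section 5e pays in full for a scan visit that could not be completed, and Section 6 offers remote measures at 3 months. This part of the objection stands. For a youth's own stop, the fault is an unreconciled text with a missing procedure.

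A reader might also infer that refusing the second scan ends collection of TLFB and RAPI. No sentence says so. The 3-month remote offer shows the opposite intent, although it is worded for youth who are unable to attend and does not mention those who are unwilling.

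The word uncooperative appears in a list of conduct towards others, beside threats and violence, and can be read narrowly. That reading is reasonable, but the text does not require it and the consequence is mandatory. After the scan, few routine in-person contacts remain, so behavioural removal of a scanned youth has limited opportunity to occur. That is also correct.

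Two further inferences fail. Not every terminated youth has BOLD data, since Session 1 precedes the scan. Nor can any fraction of the 39 budgeted losses be counted as recoverable: they are all-cause, and remote follow-up is already offered to everyone at 6 and 12 months.

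Ending contact after full withdrawal by a youth, or by a minor's parent, is proper. None of these replies answers the missing age limit in the parent rule.

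**Conclusion.** The point holds in a limited form. The conflict between the parent rule and the consent rules is plain in the text for participants aged 18 or over. Mandatory removal of an uncooperative youth, without an outcome-only path, is an avoidable source of missing outcomes that may be selective. The missing partial-withdrawal text would, alone, be only a gap in detail.

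For one youth the loss is up to three outcome visits. The total is unknown because the documents give no count of such removals. Selection bias is plausible but unquantified. A reader might conclude that 243 is too few. The documents do not support that, because the figure reproduces and already allows for 16% loss.

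The verdict rests on three assumptions: that adolescent in the parent rule means the sample as described in Section 2; that the consent pages, which were not available for this review, do not supply the missing limits; and that some removed youth would answer remotely. The change should be made because it is cheap and affects who stays in follow-up.

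**What to change.** Amend the two withdrawal paragraphs of Section 6 as follows.

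1. Limit the parent rule to youth who are 17 or under at the time of the request.
2. State that declining a scan, session, sample or question is neither withdrawal nor uncooperative conduct, and that these youth are still offered TLFB and RAPI by the existing phone/REDCap route.
3. For youth removed from in-person sessions for disruptive or uncooperative conduct, offer remote outcome follow-up. Leave cases of threats or violence to staff-safety and IRB judgement.
4. Record the level of withdrawal (one component, in-person visits, or all contact) and the reason.

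Full withdrawal by the youth, or by a minor's parent, still ends all contact. The consent forms should be checked for consistency with the new wording.

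The cost is a wording amendment, a disposition field and a few more remote contacts. Enrolment and the content of either intervention do not change.
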